We found that F-DOPA PET substantiated a lesion seen on CT and/or MRI scan in 6 of 11 patients, including some with questionable results on conventional imaging. We amended the protocol in 2008 to administer carbidopa, 200 mg, one hour before the study. [name] has found that this strategy improves tumor detection of pheochromocytoma, presumably by inhibiting decarboxylation of the tracer. This amendment will now allow us to perform FDOPA PET/CT, which was not available previously.

The project was amended in 2004 regarding the routine chest MRI scans. We initially obtained images on a 0.5 T magnet using, using STIR, T1 and T2 images. Subsequently a 1.5 T magnet replaced the lower strength magnet and STIR images were not obtained. Recently a 3.0 T magnet has become available with image acquisition gated to the EKG R-R interval so that artifact from cardiac motion is reduced. Our collaborator [name] has performed T1 and T2 sequences using this approach with excellent resolution of mediastinal and chest structures. Increased strength of magnetic field compared to conventional 1.5T MRI allows for a stronger signal and therefore improved signal to noise ratio. Free breathing techniques are used to avoid breath holding, which may be difficult for those patients with volume overload. The combination of higher signal and decreased motion artifacts should significantly improve resolution allowing for better delineation of small lesions that may be responsible for ectopic ACTH production. To test this, we have added these sequences.

We wish to clarify the use of chest CT scans, as the available modalities have changed. A “surgical chest protocol CT” (which involves thin (1-2mm) cuts throughout the thorax) will be obtained at each visit.

For the initial imaging, gated “cardiac CT” will be obtained as well to look for retrocardiac lesions that can be obscured by non-gated routine CT. However, because of the amount of radiation, we will obtain this scan only at the initial visit, unless there is a subsequent clinical suspicion of a retrocardiac lesion.

OBJECTIVES

Specific questions to be addressed:

F-DOPA PET/CT

(a) Compared to other imaging techniques, is the sensitivity and specificity of F-DOPA PET/CT higher in detecting the source of ectopic ACTH production in patients with known and unknown tumor localization?

(b) Does a correlation exist between F-DOPA uptake and the type of tumor, its size and proliferative activity?

Octreoscan

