(c) Can the administration of mifepristone, 600 mg daily for 10 days, convert a negative standard 6 mCi OCT (L-OCT) to a subsequent positive result?

MRI

(d) Does gated chest MRI detect more lesions than routine MRI?

STUDY DESIGN AND METHODS

Standard Medical Evaluation of Cushing Syndrome

We will evaluate patients at the Clinical Center on an inpatient ward. Each subject will undergo a complete medical history, physical examination, and chemical screening tests, including acute care panel, liver function tests, thyroid function tests, complete blood count, plasma ACTH levels (30 ml of blood), and urine free cortisol. Patients also undergo measurement of diurnal cortisol in blood and saliva to confirm the diagnosis of Cushing syndrome (20 ml of blood). This is followed by a CRH stimulation test (30 ml of blood), inferior petrosal sinus sampling (IPSS; 90 ml of blood) and 8 mg overnight dexamethasone suppression test (10 ml of blood). Patients undergo MRI before IPSS: those with a mass greater than 6 mm diameter may not need IPSS, if CRH and dexamethasone suppression tests are compatible with Cushing's disease. All of these tests are performed as part of the standard evaluation of Cushing syndrome.

The initial diagnostic evaluation lasts up to 14 days. Where not limited by medical or social concerns, and where guesthouse accommodation is available, it may be performed in the outpatient/day hospital areas except for overnight stays associated with diurnal sampling. Patients whose results are consistent with Cushing's disease will be referred for transsphenoidal surgery, and will not undergo the imaging studies described below.

Patients whose evaluation indicates ectopic ACTH secretion (generally, lack of response to CRH, dexamethasone and lack of central to peripheral ACTH gradient on IPSS) will undergo standard, medically-indicated, imaging studies for localization of the tumor, including CT (neck, chest, abdomen, and pelvis), 1.5 T MRI (neck, chest, abdomen, and pelvis), and 6 mCi standard Octreoscan (L-OCT). Women will undergo a serum pregnancy test within 24 hrs before administration of any isotope.

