(a) *Compared to other imaging techniques, is the sensitivity and specificity of F-DOPA PET/CT higher in detecting the source of ectopic ACTH production in patients with known and unknown tumor localization?* To determine this, we will calculate the sensitivity, specificity, positive and negative values in patients with proven tumors and compare these with the results from the other modalities. Confidence intervals will be calculated and overlapping results will indicate that the modalities are similar. We cannot perform these calculations for unknown tumors, but can compare the overall percentage of tumors found of all imaged using each technique.

(b) *Does a correlation exist between F-DOPA uptake and the type of tumor, its size and proliferative activity?* To do this, we will evaluate the percent of each type of tumor that has a positive F-DOPA scan. Confidence intervals will be used to compare across tumor types. Univariate logistic regression will be performed using size and mitotic index as the variables.

(c) *Can the administration of mifepristone, 600 mg daily for 10 days, convert a negative standard 6 mCi OCT (L-OCT) to a subsequent positive result?* This will be a descriptive analysis, indicating the percentage of tumors that convert the test to a positive result. A post-hoc analysis will compare this percentage to the historical percentage of tumors that are positive on high but not low dose octreoscan.

(d) *Does gated chest MRI detect more lesions than routine MRI?* A similar approach will be used, to look at the percentage of known tumors that are detected by gated vs routine MRI and comparing confidence intervals around those values.

PHARMACEUTICAL AND RADIATION SAFETY

Pharmaceutical Information: F-DOPA

F-DOPA is a radiolabeled amino acid (^{18}F has a 109 minute half-time). It is approved by the FDA for use under IND # 35513. [name], Chief, PET Department, holds the IND. F-DOPA is produced as outlined in the IND. F-DOPA has been used in many protocols at the NIH and at other centers throughout the world. The formulation is prepared on the day of use and assayed in a dose calibrator. The total amount of F-DOPA will typically be ~2.4 mg and will not exceed 6.5 mg.

Pharmaceutical Information: [^{111}In -DTPA-D-Phe]-pentetreotide

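### Objective (d) compares gated and routine chest MRI through separate confidence intervals without requiring that the same tumors had both scans, so it ignores the pairing the design provides

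*Combined protocol and SAP*

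**What the plan says.** Under OBJECTIVES, item (d) asks "Does gated chest MRI detect more lesions than routine MRI". Neither a scanner nor a period is named for routine MRI.

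Under ANALYSIS OF THE STUDY, Data Collection and Evaluation, the method for (d) is "to look at the percentage of known tumors that are detected by gated vs routine MRI and comparing confidence intervals around those values". It is described as similar to what precedes it. The only rule given for reading compared intervals is in (a), where overlap is taken to mean that the modalities are similar. The same section names McNemar's test for paired data and presents the methods for (a) to (d) as additions to it.

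The INTRODUCTION gives the scanner history. The earliest chest scans were made at 0.5 T and included STIR. Of the next stage it says "Subsequently a 1.5 T magnet replaced the lower strength magnet and STIR images were not obtained". The latest stage is cardiac-gated imaging at 3.0 T, and here the plan says "To test this, we have added these sequences".

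For current patients, Standard Medical Evaluation of Cushing Syndrome lists 1.5 T MRI, including the chest, as standard imaging once ectopic ACTH secretion is indicated. Research Procedures adds a gated 3 T chest MRI.

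**The concern.** The design gives two scans of the same chest in the same patient, which is the efficient way to compare two imaging techniques. The method written for (d) sets this aside. It takes one percentage per technique, puts an interval round each, and compares the two intervals as if they came from independent groups.

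Two things are at stake.

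1. **Sensitivity of the comparison.** Overlap of separate intervals is a blunt criterion for paired data. It can give a verdict of similar when the discordant tumors point clearly one way. McNemar's test is also named, so the plan could produce two conflicting answers, and it does not say which governs.

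2. **The denominators.** Nothing in (d) requires both scans, sets a time window, or excludes routine scans made before gated MRI existed. The two percentages may therefore rest on different tumors.

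**Working it through.** The documents give no detection rate, sample size or power for (d), so there is no stated figure to reproduce. All counts below are assumptions chosen to show how the methods behave.

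**Step 1: separate intervals against the paired test.** Assume 30 tumors with both scans: 15 seen on both, 6 on gated only, 0 on routine only and 9 on neither.

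- Routine: 15/30 = 50%, Clopper-Pearson 95% interval 31% to 69%.
- Gated: 21/30 = 70%, interval 51% to 85%.
- The intervals overlap between 51% and 69%, so the reading rule in (a) would call the techniques similar.
- Exact McNemar on the 6 discordant tumors: p = 2 x (1/2)^6 = 0.031.
- Paired difference: (6 - 0)/30 = 20 points. Simple large-sample standard error: sqrt(6 - 6^2/30)/30 = sqrt(4.8)/30 = 0.073. Approximate 95% interval: 20 +/- 1.96 x 7.3, or about 6 to 34 points, which excludes zero. This formula is rough when one discordant cell is empty.

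**Step 2: the two percentages do not settle the paired result.** Keep 15/30 and 21/30 but let the discordant tumors split 7 to 1. Exact McNemar is then 2 x (1 + 8)/2^8 = 18/256 = 0.070. The same percentages and the same separate intervals go with p = 0.031 or p = 0.070, depending on a table that (d) does not ask for. Six discordant tumors, all in one direction, is the smallest count that gives p below 0.05; five give p = 0.0625.

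**Step 3: what mixed denominators could do.** Suppose gating and 3 T add nothing over 1.5 T. Let w be the share of routine scans made at 0.5 T, and let s1.5 and s0.5 be the routine detection rates. The apparent gain for gated MRI is then

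w x (s1.5 - s0.5).

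For an assumed gap of 20 points this is 5 points at w = 25%, 10 at 50% and 15 at 75%. If the STIR images made the 0.5 T scans better, the sign reverses. With same-episode pairs, w = 0 and the term is zero whatever the gap. The documents report 89 patients enrolled but give neither w nor the rates.

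**The case against.** The strongest defense is that the plan already points to a concurrent, paired comparison. Both scans are scheduled for current patients, and McNemar's test, which admits only tumors with both results, is named ahead of all four objectives. The rationale in the INTRODUCTION sets 3 T against conventional 1.5 T, not against 0.5 T. Objective (c) names a historical comparator explicitly; (d) does not.

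Most of this stands, and it rules out a stronger reading. A reader might infer from the scanner history that (d) will pool early and current routine scans and so confound gating with calendar period. The documents do not support that. Routine MRI had two configurations, the third being the gated scan itself, and no section says that old scans will be pooled. The first gated scan is also not clearly dated: the paragraph that describes it opens with "The project was amended in 2004 regarding the routine chest MRI scans", while the reference list runs to 2012. The share of tumors that predate gating could be small.

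The defense does not cover the percentages and intervals that (d) says it will compare. Naming McNemar's test alongside them does not restrict them to tumors with both scans. Nor does it define a pair. Under Evaluation and treatment at the conclusion of imaging episodes, non-localized patients return for MRI every 6 to 12 months, so one tumor may have several routine scans. Under Adverse events and monitoring plan, leaving out some imaging counts as a minor deviation, so denominators can differ even among current patients.

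**Conclusion.** The point holds as a weakness of method and an undefined analysis set. It is not a demonstrated bias. Comparing separate intervals discards the pairing and can miss a difference that the paired analysis would show. The 15/30 and 21/30 example establishes that this can happen, not that it will in this trial. Entry of earlier routine-only scans is possible on the literal wording, but its likelihood, size and direction are unknown; the Step 3 figures rest wholly on assumed inputs.

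One limit remains even with perfect pairs. The two scans differ in field strength as well as gating, and the INTRODUCTION expects both to help. The data can support a statement about gated 3 T against ungated 1.5 T MRI, but a reader might wrongly take a positive result as the effect of gating alone.

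**What to change.** Amend the text of (d) as follows:

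- Define routine MRI as the 1.5 T chest scan from the same imaging episode as the gated 3 T scan, and state which episode counts if a tumor has more than one.
- Restrict the percentages and McNemar's test to known tumors with both scans.
- Report the 2x2 detection table and the paired difference with its confidence interval, by a method suited to small counts, in place of comparing separate intervals.
- Word the conclusion as gated 3 T versus ungated 1.5 T chest MRI.

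The cost is a few lines of analysis text and no new scans. Tumors with only a routine scan leave the (d) denominator, so the routine interval is wider. Those tumors carry no within-patient information on gated versus routine MRI, and they can still be described separately.
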